3.4. Rationale for JTJH Amendment (a)

Amendment (a) was developed to address requests resulting from member states participating in the Voluntary Harmonisation Procedure during the assessment of the initial clinical trial application for Study JTJH in the European Union. At the member states' request, the protocol was modified to incorporate those states' recommendations in the inclusion and exclusion criteria and to establish the actions to be taken in case of prolongation of the QT/QTc interval >480 msec. Because a protocol amendment was required, the opportunity was taken to also include several other minor protocol improvements and clarifications.

6.1 Inclusion Criteria

...

[8] men must be sterile or agree to use an effective method of contraception or a highly effective method of contraception during the study and for at least 12 weeks following the last dose of LY2606368

Refer to Appendix 1 for definitions of fertile men, effective method of contraception, and highly effective method of contraception.

[9] women of childbearing potential must:

- a. have a negative serum pregnancy test at the baseline visit
- b. have a negative urine pregnancy test within 7 days prior to the first dose of LY2606368
- c. agree to use a highly effective method of contraception (Appendix 1) during the study and for 12 weeks following the last dose of LY2606368
- d. not be breast-feeding

Refer to Appendix 1 for definitions of women of childbearing potential and postmenopausal women.

6.2 Exclusion Criteria

...

[11] have symptomatic central nervous system (CNS) malignancy or metastasis. Asymptomatic patients with treated CNS metastases are eligible for this study if they are not currently receiving corticosteroids to treat CNS metastases, and/or anticonvulsants. CNS metastases should be stable for at least 14 days by clinical assessment, and patients should not have received corticosteroids to treat CNS metastases within 14 days of the first dose of study drug.

...

[14] have previously completed or withdrawn from this study or any other study investigating LY2606368 or a CHK1 inhibitor or have shown hypersensitivity to any of the components of the LY2606368 formulation

...

[16] have a symptomatic human immunodeficiency virus (HIV) infection or symptomatic activated/reactivated hepatitis A, B, or C (screening is not required). If the medical history, symptoms, and/or laboratory values suggest that the patient may have HIV or hepatitis A, B, or C, appropriate assessment should be conducted to determine whether the patient should be excluded.

7.4 Dosage Modification

Before the start of each cycle:

- Nonhematologic toxicities must resolve to Grade 0 or 1 or baseline, except AEs with no immediate medical consequence or those that can be controlled with adequate treatment (for example, alopecia, fatigue, nausea, vomiting, diarrhea, or asymptomatic changes in electrolytes).
- Neutropenia, thrombocytopenia, and anemia must resolve to Grade 0, 1, or 2, as shown in Table JTJH.7.2.

Table JTJH.7.2. Hematologic Parameters Required for the Start of Each Cycle

	Dose
Neutrophils	≥1000/mm³
Platelets	>75/mm³
Hemoglobin	≥8 g/dL

Treatment may be delayed for a maximum of 14 days to allow a patient sufficient time for recovery from LY2606368-related toxicity. If a patient does not recover from the toxicity within 28 days from the time of last treatment, the patient should be discontinued from LY2606368. In exceptional circumstances, a longer delay is permitted upon agreement between the investigator and the Lilly clinical research physician (CRP).

If a patient, in the investigator's opinion, experiences a toxicity warranting a dose reduction, LY2606368 should be reduced as shown in Table JTJH.7.3.2.

Table JTJH.7.2.3. LY2606368 Dose Reductions

Reduction	Dose
1 st LY2606368 dose reduction	80 mg/m ²
2 nd LY2606368 dose reduction	60 mg/m ²
3 rd LY2606368 dose reduction	Discontinue from LY2606368

7.5.2. LY2606368 Lactate Monohydrate

A 67-mg strength of LY2606368 lactate monohydrate drug product is in development and may be used in Study JTJH. The vial will contain a slight excess to facilitate the withdrawal of the label amount 67 mg/vial for use with an appropriate device, such as an infusion set. ~~The drug product is stable when stored at room temperature.~~ Reconstituting the vial contents with water for injection yields a clear yellow solution with a concentration of 3.35 mg/mL of LY2606368. For the most current detailed information on this strength refer to the IB and Pharmacy Binder.

7.8.1 Continued Access

Patients who are still on LY2606368 at the time of study completion may continue to receive LY2606368 if they are experiencing clinical benefit and no undue risks. The continued access period will apply to this study only if at least 1 patient is still on LY2606368 when study completion occurs. Lilly will notify investigators when the continued access period begins. Lilly may allow patients to enroll in a LY2606368 “rollover” protocol to provide long-term continued access for patients enrolled in this study. ~~Patients must sign a new ICF before continued access is provided.~~ The continued access period is shown in Figure JTJH.7.1.

9.1 Efficacy Assessments

Tumor assessments will be performed for each patient at the times shown in the Schedule of Activities (Section 2).

Computed tomography (CT) scans, including spiral CT, are the preferred methods of measurement (CT scan thickness recommended to be ≤ 5 mm); however, magnetic resonance imaging (MRI) is also acceptable in certain situations, such as when body scans are indicated or if there is a concern about radiation exposure associated with CT. Intravenous and oral contrast is required unless medically contraindicated.

The CT portion of a positron emission tomography (PET)-CT scan may be used as a method of response assessment if the CT is of identical diagnostic quality to a diagnostic CT (with IV and oral contrast). A PET scan alone or as part of a PET-CT may be performed for additional analyses but cannot be used to assess response according to RECIST v.1.1 (Eisenhauer et al. 2009).

Radiologic scans of the thorax and abdomen are required. A baseline intracranial evaluation with CT or MRI should be conducted. Scans of the pelvis or bone scans should be performed if clinically indicated. Copies of the scans may be requested by the sponsor for central review.

See Section 10.3.1 for definitions of the efficacy endpoints.

9.4.1 Other Safety Measures

For each patient, safety assessments, including ECGs, vital signs, and laboratory tests, should be collected as shown in the Schedule of Activities (Section 2). ECGs should be recorded according to the study-specific recommendations that will be provided separately.

As of 27 August 2015, no patients treated with LY2606368 monotherapy have had an average QTcF interval >480 msec at any time point. However, if a patient experiences a QTcF interval >480 msec, the patient should be monitored for signs of life-threatening arrhythmias such as torsades de pointes. It should be confirmed that the measurement is correct by repeating the ECG and ruling out other causes such as atrial fibrillation or the presence of a pacemaker. If the result is confirmed, institutional guidelines or standard of care measures for management of QTcF interval >480 msec and/or associated arrhythmias should be initiated. These actions may include the administration of IV magnesium sulfate and the assessment of clinical chemistry. If electrolytes are abnormal, they should be repeated as indicated. The QTcF value should be

monitored until the interval has returned to <480 msec or at least to predose levels. It is recommended that the patient be assessed by a cardiologist before leaving the treating facility. For all subsequent doses, an ECG must be obtained at 10 minutes after the end of infusion (EOI) (± 5 minutes), 30 minutes after EOI (± 10 minutes), and >1 hour after EOI.

If a patient experiences a QTcF interval >500 msec and has an associated life-threatening arrhythmia, he/she should be discontinued from study treatment. If a patient experiences a QTcF interval >500 msec without an associated life-threatening arrhythmia and if the investigator deems it in the best interest of the patient, the patient may continue treatment with LY2606368. If a patient has a second occurrence of QTcF interval >500 msec, he/she should be discontinued from study treatment.

Any clinically significant findings that result in a diagnosis and that occur after the patient receives the first dose of LY2606368 should be reported to Lilly or its designee as an AE via CRF/electronic data entry/designated data transmission methods.

9.5 Pharmacokinetics

...

These samples will be analyzed at a laboratory designated by the sponsor by using a validated liquid chromatography–mass spectrometry/mass spectrometry (LC-MS/MS) method.

...

9.8 Biomarkers

Biomarker research is performed to address questions of relevance to drug disposition, target engagement, mechanism of action, variability of patient response (including safety), and clinical outcome. Sample collection is incorporated into clinical studies to enable examination of these questions through measurement of biomolecules including DNA, RNA, proteins, lipids, and other cellular elements.

As part of Lilly's ongoing efforts to understand the relationship between cancer, genetics, and response to therapy, this study will analyze biomarkers relevant to the mechanism of action of CHK1, DNA damage response pathways or downstream effects, cell cycle markers, immune function, and cancer pathobiology and/or for related research methods or validation of diagnostic tools or assays.

Samples for biomarker research will be collected as specified in Section 2 where local regulations allow. It is possible that biomarker data for patients in the study have already been generated from samples that were collected and analyzed before the patients' enrollment in this trial. This may include data generated from genetic analyses. If available, these data may be requested from medical records for use in the research described in Sections 9.8.1 and 9.8.2.

Samples for biomarker research will be collected as specified Section 2, where local regulations allow.

10.3.4. Interim Analyses

For each cohort, one interim analysis of fertility will be conducted after the 29th patient in the cohort has completed Cycle 3, and, if required, the response is confirmed. The interim analysis will be conducted to assess whether the respective cohort is unlikely to achieve statistical significance on its primary endpoint and may also include PK data in order to confirm that patients are in the expected exposure range.

The stopping rule for interim analysis ~~and final analysis~~ is defined as follows:

...

Appendix 1 Abbreviations and Definitions

fertile men

A man is considered fertile after puberty unless permanently sterile by bilateral orchidectomy.

**women of
childbearing
potential**

A woman is considered of childbearing potential (ie, fertile), after menarche and until becoming postmenopausal unless permanently sterile. Permanent sterilization methods include hysterectomy, bilateral salpingectomy, and bilateral oophorectomy.

A postmenopausal state is defined as no menses for 12 months without an alternative medical cause. A high follicle-stimulating hormone level in the postmenopausal range may be used to confirm a postmenopausal state in women not using hormonal contraception or hormonal replacement therapy; however, in the absence of 12 months of amenorrhea, a single follicle-stimulating hormone measurement is insufficient.

4.1. Primary Objective

- Cohort 1: To estimate the overall response rate (ORR) when a dose of 105 mg/m² LY2606368 every 14 days is administered to patients with ED-SCLC that have platinum-sensitive disease
- Cohort 2: To estimate the ORR when a dose of 105 mg/m² LY2606368 every 14 days is administered to patients with ED-SCLC that have platinum resistant/refractory disease

4.2. Secondary Objectives

- To characterize the safety and toxicity profile of LY2606368
- To characterize the pharmacokinetics (PK) of LY2606368
- To estimate secondary efficacy measures including disease control rate (DCR), duration of response (DoR), progression-free survival (PFS), and overall survival (OS)
- To evaluate the association between best tumor response and change from baseline in lung cancer specific-symptoms, symptomatic distress, activity status, overall quality of life, total Lung Cancer Symptom Scale (LCSS) score, and Average Symptom Burden Index (ASBI) for patients who have platinum-sensitive or platinum resistant/refractory SCLC

4.3. Exploratory Objectives

- To explore biomarkers associated with the efficacy and safety of LY2606368, the exposure (PK) of LY2606368, the mechanism of action of CHK1, DNA damage response pathways or downstream effects, cell cycle markers, immune function, or cancer pathobiology
- To explore whether ongoing measurement of tumor shrinkage (such as changes in tumor size) correlate with efficacy measures

5. A Priori Statistical Methods

5.1. General Considerations

Statistical analysis of this study will be the responsibility of Eli Lilly and Company. The interpretation of the study results will be the responsibility of the Lilly Clinical Research Physician/Clinical Research Scientist (CRP/CRS) and statistician. The CRP/CRS and statistician will also be responsible for the appropriate conduct of internal reviews for both the final study report and any study-related material to be authorized by Lilly for publication.

Any change to the data analysis methods described in the protocol will require an amendment ONLY if it changes a principal feature of the protocol. Any other change to the data analysis methods described in the protocol and the justification for making the change will be described in the clinical study report.

The study will enroll approximately 116 patients (58 platinum-sensitive patients, 58 platinum-refractory/resistant patients).

For the platinum-sensitive cohort, it is assumed that a true ORR of less than 20% indicates inadequate antitumor activity. Given that a futility interim analysis will be conducted on the first 29 patients' response data, then with a one-sided significance level of 0.1, a sample size of 58 patients will provide approximately 90% power to detect a true ORR of at least 35%.

For the platinum-refractory/resistant cohort, it is assumed that a true ORR of less than 5% indicates inadequate anti-tumor activity. Given that a futility interim analysis will be conducted on the first 29 patients' response data, then with a one-sided significance level of 0.1, a sample size of 58 patients will provide approximately 90% power to detect a true ORR of at least 15%.

The stopping rule for interim analysis and decision rule for final analysis are defined as follows:

- Platinum-sensitive cohort:
 - If 4 or fewer overall responses of confirmed CR or PR are observed in the first 29 patients, then the cohort will be terminated for futility; otherwise, the cohort will continue
 - If 16 or more overall responses of confirmed CR or PR are observed in all 58 patients, then the ORR is statistically significantly greater than 20%
- Platinum-refractory/resistant cohort:
 - If no overall response of confirmed CR or PR is observed in the first 29 patients, then the cohort will be terminated; otherwise, the cohort will continue
 - If 6 or more overall responses of confirmed CR or PR are observed in all 58 patients, then the ORR is statistically significantly greater than 5%

For each cohort, the overall type II error rate, i.e. the probability of terminating an effective cohort, will be controlled using a Lan-DeMets spending function (Lan and DeMets 1983), which generates boundaries that are very similar, though not identical, to the classical stopping

boundaries of O'Brien and Fleming (1979). The type II error rate spent at interim analysis after the first 29 patients for each cohort is approximately 2%; the cumulative type II error rates spent at final analysis for platinum-sensitive cohort and platinum-refractory/resistant cohort are 9.9% and 9.4%, respectively.

The following patient populations will be analyzed in this study:

- **Full analysis set:** will include all enrolled patients. This population will be used for all baseline, efficacy, health economics, dosing/exposure, and safety analyses
- **Per-protocol population:** will include all enrolled patients who do not have any major protocol violations that could potentially affect the efficacy conclusions of the study. This population will be determined after study team review of the list of important protocol deviations at end of the study, following the guideline below:
 - Patients who either have a post-baseline tumor assessment (radiological imaging and/or tumor measurement [palpable or visible]) of any level of response (excluding “not evaluable”), or discontinue from study treatment prior to tumor assessment due to an AE
 - The absence of the violation of inclusion/exclusion criteria, significant deviations in efficacy assessments, and instances of suspected misconduct
- **Pharmacokinetic population:** will include all enrolled patients who received at least 1 full infusion (dose) of LY2606368 and have evaluable PK samples collected
- **Biomarker population:** will include the subset of patients from the full analysis set from whom a valid assay result has been obtained

Unless otherwise stated, all confidence intervals (CIs) will be given at a 2-sided 95% level.

Summary statistics for continuous variables will include number of patients (N), mean, median, standard deviation (SD), minimum, and maximum. Summary statistics for categorical endpoints will include N, frequency, percentages, and associated SE and 95% CI. Exploratory analyses will be conducted as deemed appropriate. Time-to-event variables will be summarized using the Kaplan-Meier (KM) method. Kaplan-Meier estimates of median and quartiles will be reported along with 95% CIs.

Analyses will be implemented using Statistical Analysis System (SAS[®], SAS Institute) version 9.1 or higher; any exceptions will be documented in the outputs.

The following data handling conventions will be used in the analysis (see [Table JTJH.5.1](#)).

Table JTJH.5.1. Data Handling Conventions

Term	Definition or Rule
Relative Study Day	If assessment is on or after date of first dose then (date of assessment) – (date of first study treatment dose) +1
	If assessment precedes first dose of drug then (date of assessment) – (date of first study treatment dose)
	There is no Study Day 0. Study Day 1 is the date of first dose and study day -1 is the day before the first dose.
Baseline	For change from baseline analyses, baseline value is defined as the last reported measure on or before the first dose date (prior to the dose administration), unless otherwise specified. For change from baseline within a cycle, baseline value is defined as the measure prior to the first dose of that cycle, unless otherwise specified.
Entered	Patients who have signed the informed consent form directly or through their legally acceptable representatives.
Enrolled	Patients who have been assigned to study treatment and have received at least one dose of study treatment.
Screen Failures	Patients who have signed informed consent, do not meet eligibility criteria and are not enrolled.

5.2. Adjustments for Covariates

Please refer to Sections [5.11](#) and [5.17.1](#) for analyses with adjustments for covariates.

5.3. Handling of Dropouts or Missing Data

The full analysis set, which includes all enrolled patients, will be used for all baseline, efficacy, health outcomes, dosing/exposure, and safety analyses.

Baseline will refer to the last non-missing observation prior to first administration of any treatment unless stated otherwise. Missing data, except for dates, will not be imputed. When dates are used in calculations, missing days will be replaced with 15th of the month and missing day/month with 01 JULY. Where windows are allowed for data collection and there is more than one reading in any window, appropriate consideration will be given as to whether only one value from the window should be used, and if so how it should be chosen. This could either be the mean (geometric mean) or the value closest to the mid-point of the window or the value closest to the data collection time of another variable if the analysis involves time-matched analyses.

If a patient discontinues from study treatment for any reason other than becoming lost to follow-up or death, regular follow-up visits will be conducted to collect information on subsequent non-protocol defined therapy, first disease recurrence, and death. Therefore, it is possible to obtain information for time-to-event endpoints for these patients.

In the primary efficacy analysis, a patient with a tumor response of “not evaluable” will be included in the denominator for the purpose of calculating ORR.

In the health outcomes/quality-of-life analyses, if any of the 6 symptom-specific questions have not been completed, the ASBI will not be calculated. Similarly, if any of the 9 LCSS questions have not been completed, the total LCSS score will not be calculated.

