8.3. Lost to Follow-Up

A patient will be considered lost to follow-up if he or she repeatedly fails to return for scheduled visits and is unable to be contacted by the study site. Study site personnel are expected to make diligent attempts to contact patients who fail to return for a scheduled visit or who the site is otherwise unable to follow-up.

Study site personnel, or an independent third party, will attempt to collect the survival status for all enrolled patients who are lost to follow-up, within legal and ethical boundaries. Public sources may be searched for survival status information. If the patient's survival status is determined, the survival status will be documented, and the patient will not be considered lost to follow-up.

Lilly personnel will not be involved in any attempts to collect survival status information.

9. Study Assessments and Procedures

Section 2 provides the Schedule of Activities for this study.

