5.10.2. Secondary Efficacy Analyses

Secondary efficacy variables are defined as follows:

Disease control rate is defined as the number of patients who achieve a BOR of CR, PR, or stable disease (SD) divided by the total number of patients enrolled to the corresponding cohort (full analysis set). The confirmation of CR and PR is required. The BOR for patients with an unconfirmed PR or CR observation will be classified as SD, as long as they otherwise meet those requirements (see following sentence). In the case of SD, measurements must have met the SD criteria at least once after study entry at a minimum interval (not less than 5 weeks). The DCR, with exact 95% CI, will be summarized for each cohort using the Clopper-Pearson method.

Duration of response is defined as the time from the date measurement criteria for CR or PR (whichever is first recorded) are first met until the first date that disease is recurrent or objective progression is observed, per RECIST 1.1 criteria, or the date of death from any cause in the absence of objectively determined disease progression or recurrence.

Overall survival is defined as the time from enrollment until death from any cause. If the patient is alive or lost to follow-up at the time of data analysis, OS data will be censored on the last date the patient is known to be alive. Overall survival curves, median OS, and OS rates at various time points with 95% CI, for each cohort will be estimated using the Kaplan-Meier method (Kaplan and Meier 1958).

Progression-free survival is defined as the time from enrollment until the first radiographic documentation of progression or death from any cause in the absence of PD. Patients known to be alive and without disease progression will be censored at the time of the last adequate tumor assessment prior to study completion (a detailed PFS event/censoring scheme is provided in [Table JTJH.5.2](#)). Progression-free survival curves, median PFS, and PFS rates at various time points with 95% CI for each cohort will be estimated using the Kaplan-Meier method (Kaplan and Meier 1958).

Table JTJH.5.2. PFS Event/Censoring Scheme

Situation ^a	Event/Censor	Date of Event or Censor
Tumor progression or death	Event	Earliest date of PD or death
No tumor progression and no death	Censored	Date of last adequate radiological assessment or date of enrollment (whichever is later) ^b
Unless		
No baseline radiological tumor assessment available	Censored	Date of enrollment

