5.13.2. Adverse Events

All patients who receive at least one dose of study treatment will be evaluated for safety and toxicity. Adverse event terms and severity grades will be assigned by the investigator using CTCAE v4.0X. In addition, AE verbatim text will also be mapped by the sponsor or designee to corresponding terminology within the Medical Dictionary for Regulatory Activities (MedDRA). Adverse events will be reported using a unified CTCAE/MedDRA reporting process:

- The CTCAE v4.0 term reported by the investigator will be mapped to the MedDRA preferred term (PT) and system organ class (SOC) of the corresponding MedDRA lowest level term (LLT), unless the reported CTCAE term is ‘Other – specify’
- If the reported CTCAE term is ‘Other – specify’ the MedDRA LLT, PT and SOC mapped from the verbatim AE term will be used
- All listings and summaries will use the MedDRA LLT and the MedDRA PT resulting from this process.

A treatment-emergent adverse event (TEAE) is defined as an event that first occurred or worsened in CTCAE grade after the first dose of study treatment. The MedDRA LLT will be used in the treatment-emergent computation.

All observed AEs will be graded using CTCAE version 4.0. Adverse events, deaths and serious adverse events (SAEs) will be listed and summarized. Summaries for patients on therapy will include:

- Summary of all pre-existing conditions and AEs
- Summary of all TEAEs
- Summary of TEAEs possibly related to study treatment
- Summary of all TEAEs by maximum CTCAE grade
- Summary of TEAEs possibly related to study treatment by maximum CTCAE grade
- Summary of deaths on treatment or post-study treatment deaths possibly related to study treatment.

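### SAP 5.3 fills in partial dates without bounds, so AEs can cross the first-dose date in either direction and deaths can fall before last contact or before enrollment

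*SAP*

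**What the plan says.** SAP 5.3 makes dates the one exception to its no-imputation policy: "Missing data, except for dates, will not be imputed". The rule applies "When dates are used in calculations", and it is that "missing days will be replaced with 15th of the month and missing day/month with 01 JULY". It does not distinguish between types of date.

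The analyses that depend on these dates are:

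- **Treatment-emergent AEs (SAP 5.13.2).** A treatment-emergent AE is "an event that first occurred or worsened in CTCAE grade after the first dose of study treatment".
- **OS (SAP 5.10.2).** "Overall survival is defined as the time from enrollment until death from any cause". For patients without a death, "OS data will be censored on the last date the patient is known to be alive". The last-alive date serves only for censoring; it is not a floor for a death date.
- **PFS (SAP Table JTJH.5.2).** The event date is the earlier of progression and death. The later-of-two-dates wording in that table sets censoring dates and the start of the scan-interval count. It does not bound an imputed event date.

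SAP Table JTJH.5.1 (data handling conventions) adds no bound. Protocol 8.3 allows survival status to be sought outside the clinic: "Public sources may be searched for survival status information". A patient whose status is found in this way is no longer treated as lost to follow-up, so the death enters the analysis as an event.

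**The concern.** A midpoint rule is reasonable when nothing else is known about the date. Here something else usually is known: the first-dose date, the enrollment date and the last contact. The rule ignores all three, so it can produce a date that the patient's own record rules out.

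For safety, an early on-treatment event can leave the treatment-emergent tables, or a screening event can enter them, because of where the first dose fell in the calendar month. For survival, a patient can be given a death before a visit at which they were alive, or before they joined the study. Each cohort has only 58 patients, so a few such records could matter. If the plan gives no bound, the correction will be chosen during programming, with open-label data in view.

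**Working it through.** The plan states no figure on this point, so there is none to reproduce. The check applies the rule literally. Enrollment is taken as the first-dose date, because SAP Table JTJH.5.1 counts a patient as enrolled only once dosed.

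**1. On-treatment AE, day missing**

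- Example: first dose 21 March 2016, AE on 28 March, recorded as March 2016. The imputed onset is 15 March, and 15 − 21 = −6 days. By its onset date the AE is not treatment-emergent.
- Condition: onset in the month of first dose, and first dose on the 16th or later. In 2016, 186 of 366 days qualify (51%).
- Share, assuming first-dose day *d* uniform on 1–30 and onset uniform 0–29 days later. Same-month pairs: Σ(31 − *d*) for *d* = 1 to 30 = 465. Pairs with *d* ≥ 16: 15 + 14 + … + 1 = 120. Share = 120/465 = 25.8%.
- For an AE exactly 7 days after dosing, over all first-dose dates in 2016, 28% are placed before first dose if the day is missing and 48% if day and month are missing.

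**2. Pre-dose AE, day missing (the opposite shift)**

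- AEs are recorded from consent (Protocol 9.2), and baseline lasts up to 28 days (Protocol Table JTJH.2.1).
- Example: AE on the 5th, first dose on the 10th, day missing. The imputed onset is the 15th, so the AE becomes treatment-emergent.
- Mirror calculation, with every same-month pre-dose pair equally likely: Σ(*d* − 1) for *d* = 1 to 30 = 435. Pairs with *d* ≤ 14: 0 + 1 + … + 13 = 91. Share = 91/435 = 20.9%.

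**3. Deaths**

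- Known by month: alive on the 22nd, died later that month. The imputed death is the 15th, 7 days before the patient was last known alive.
- Known by year: first dose 5 September 2016, death 20 November 2016. The imputed death is 01 July, 30 + 31 + 5 = 66 days before first dose, so OS is −66 days.
- Largest error: up to 16 days back or 14 forward for a missing day; up to 183 days back (31 December to 01 July) or 182 forward for a missing day and month.
- Yardstick: the 25.0-week topotecan median in Protocol 3.1 is 25.0 × 7 = 175 days.

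How often this happens, *given* a partial death date, was simulated with 100,000 patients, enrollment uniform over 2016, exponential survival with a 25-week median (assumed range 13 to 40), and contact every 14 days (the treatment cycle) or 60 days (long-term follow-up):

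| Missing | Before last contact, 60-day | Before last contact, 14-day | Before enrollment (median 13 to 40 weeks) |
|---|---|---|---|
| Day | 6.7% | 26.3% | 1.4% (2.7% to 0.9%) |
| Day and month | 42.1% | 48.0% | 14.5% (23.0% to 9.9%) |

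**4. PFS.** SAP Table JTJH.5.2 censors an event that comes two or more scan intervals after the last adequate assessment, about 2 × 6 = 12 weeks in the first year. A shift of up to 183 days in a death date can therefore also change a patient from event to censored, or the reverse.

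**The case against.** The best case against acting is that the effect is small and confined to descriptive results.

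- **Frequency.** AEs are collected at every 14-day cycle, which limits missing days. Public sources concern only patients the site can no longer reach, and nothing says that they give partial dates. This stands: the number of partial dates is unknown.
- **Misplaced AEs do not vanish.** An AE that later worsens in grade still counts as treatment-emergent. Others remain in the summary that pools pre-existing conditions with all AEs (SAP 5.13.2). Serious AEs are in the registry summary whatever their timing (SAP 5.18). Graded laboratory values are tabulated separately (SAP 5.13.4), which matters for a drug whose main toxicity is hematologic. This also stands.
- **Progression dates.** Progression rests on scans, which normally carry full dates. The exposure in PFS and DoR is therefore mainly death without progression.
- **Decisions.** ORR and the stopping and decision rules count confirmed responses. OS, PFS and AEs are estimated or summarized without a test.

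A reader might also infer three stronger things that the documents do not support:

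- That treatment-emergent counts are biased downward overall. Step 2 of the working shows the opposite shift, and the net direction cannot be derived.
- That about a quarter of all AEs are affected. The 26% applies only to AEs with a missing day that start in the month of first dose.
- That the date error exceeds the whole expected survival because Protocol 3.1 gives 2 to 4 months. That figure is for untreated relapse. Against the treated median of 175 days, only a year-only date near the end of the calendar range exceeds it.

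None of this supplies the missing bound. The rule as written still gives impossible dates.

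**Conclusion.** The point holds as a defect in a stated rule. No bound on imputed event dates appears in SAP 5.3, Table JTJH.5.1, the AE and OS definitions or the PFS scheme. Calendar arithmetic alone shows that AEs can cross the first-dose date in both directions and that deaths can precede last contact or enrollment.

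The size is conditional on a partial date. About 26% of on-treatment AEs with a missing day in the first-dose month move before dosing (uniform assumptions). Death before enrollment is rare when only the day is missing (about 1.4%) and more common when the month is missing too (about 14%, or 10% to 23% over assumed medians of 40 to 13 weeks). The exposure is limited to the treatment-emergent summaries, OS, and the death component of PFS and DoR. It is worth correcting before database lock, but it does not threaten the primary analysis.

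**What to change.** Add bounds to SAP 5.3 by type of date:

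1. **AE onset.** If the known parts of the date are compatible with onset on or after first dose, use the later of the imputed date and the first-dose date, and count the AE as treatment-emergent. If the known parts show onset before first dose, keep it before first dose.
2. **Death.** Use the later of the imputed date and the last date known alive, never before enrollment and never after the data cut-off. The floor should be the last-alive date itself, not the day after, since a patient may be seen alive on the day of death.
3. **Dates that properly precede dosing.** Exempt diagnosis, prior therapy, pre-existing conditions and earlier concomitant medication from the first-dose floor. A blanket floor would move these to first dose and create a new error.

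Under these rules the share of on-treatment AEs placed before first dose, and of deaths placed before last contact or enrollment, is zero by construction.

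The cost is a few lines of text and routine programming. The downside is that a pre-dose AE with an ambiguous date will be counted as treatment-emergent. That is conservative for safety, and it becomes a declared convention instead of depending on the day of the month.
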